8.2.4.2 Secondary Outcomes

There will be several secondary outcome measures (see Table 6). The secondary outcomes will also be measured at both part 1 and part 2: e-triage, whilst waiting for treatment, during treatment and at discharge from treatment.

Patient Engagement

User engagement with Wysa will be assessed using a combination of complementary measures. Examining time spent using a digital health intervention is not by itself a reliable measure of effective engagement, as it cannot differentiate between users who spend a long time on the app because they're positively engaged compared to those who are frustrated and struggling to use it. Therefore, measures of app usage will also include uptake and dropout rates, and digital user feedback.

Patient experience

Wysa's acceptability will be examined through user score ratings (in app) out of a maximum of 5.

Health-related quality of life

Version number 1.1 - 25th November 2023

Work and Social Adjustment Scale [17] will be used to assess quality of life. The WSAS is a reliable measure for impairment in functioning and one of the NHS talking therapies standardised questionnaires. It provides a descriptive self-assessment of the impact of mental health difficulties in 5 dimensions: work, home management, social leisure, private leisure and personal or family relationships .

Secondary Outcome	Outcome Measure
Health related Quality of life	WSAS[17]
Patient Engagement	Referral rates Dropout / discharge reason/ did not attend rates App usage data
Patient experience	Automated review questions periodically requested during general use of the tool

Table 6. Secondary Outcome Measurements

8.3 Sample and Recruitment

8.3.1 Eligibility Criteria

8.3.1.1 Inclusion Criteria

- Willing and able to provide informed consent;
- Aged 16 years or older;
- User is confident in their ability to speak and understand English at a proficient level;
- Own an electronic device capable of supporting Wysa;
- A valid email address, NHS number; phone number
- Referred or self-referred to proceed through the standard NHS talking therapies care pathway.

8.3.1.2 Exclusion Criteria

- Patients ineligible for the standard NHS talking therapies care pathway;
- Patients with previous and current known severe and enduring mental illnesses
- Patients with current psychosis or a history of psychotic symptoms in the last 6 months
- Patients with active suicidal ideation/ intent;
- Patients with significant cognitive disorders;
- Patients with a current diagnosis of a personality disorder;
- Patients with referrals for specialist presentations of pre-existing, diagnosed conditions requiring a specialised assessment beyond the standard clinical pathway;
- Not capable of providing self-consent;

8.3.2 Sampling

8.3.2.1 Sample Size

All patients accepted by the NHS talking therapies services and meeting the inclusion criteria will be eligible for the study. A minimum of 100 patients will be recruited in order for the study to be able to conclude statistical validity. This is primarily a quantitative feasibility review with no control arm.

8.3.2.2 Sampling Technique

Part 1: Participants will be all patients who self-refer or are referred to an NHS talking therapies service and accepted into the service.

Part 2: Participants will be patients who are accepted onto the Step 2 waiting list and consent to digital treatment.

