6 STUDY FLOW CHART

Wysa is delivered as a standalone system that patients download directly onto their personal device. Wysa will be made available to patients as a self referral and clinical triage tool, and further along the care pathway will provide a range of therapist enabled computerised CBT programmes.

This study will conduct a quantitative feasibility review of Wysa as an AI therapeutic support tool across a typical care pathway in adult NHS talking therapies services. The study will take place in a collaborating NHS service utilising Wysa as an offer for all patients who have a suitable digital device.

Wysa's suite of products can be utilised at four key points in the care pathway:

- 1. Referral
- 2. Waitlist
- 3. NHS talking therapies step 2 intervention
- 4. Post discharge

The study will compare data from patients who use Wysa throughout their NHS talking therapies journey, or for at least a part of their journey, with those who do not.

Following self-referral (either using the Wysa electronic triage tool or another method such as self referral portal or email) or professional referral, the individual is provided access to the Wysa app via a download link. The patient can then use the app for support whilst waiting for their next contact with the service. Where the clinician has identified that a Wysa cCBT programme is an appropriate treatment intervention, this will be prescribed via an additional download link.

Wysa's Triage tool collects demographic and clinical patient related information via the AI chatbot. This tool will support patients to complete a referral to NHS talking therapies services, allowing the service to collect the data (via an API to their EPR system) required for a referral to be opened and a clinician to make a decision about the patient's care. Here we will review predetermined data points to understand how patients engage with the e-triage and the types of patients who utilise the tool. We will also compare the time taken for the clinician to reach a clinical outcome decision when the Wysa e-triage is completed with the time taken when a standard assessment is undertaken.

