7.2 Rationale

A key issue with current mental health service provision is lack of timely access to therapy or professional support. NHS talking therapies services are overwhelmed with high volumes of referrals, many of which are often inappropriate due to patients living out of area, or having very complex needs which are out of the scope of NHS talking therapies interventions. We predict that automations in the referral process brought about by the use of the Wysa electronic triage will result in significant administrative and clinical time savings, by enabling a large part of these assessments to take place via the app, and may also reduce the number of inappropriate referrals, due to users with complex needs or who are ineligible or at high risk being signposted to alternative services at an earlier stage. Our solution also enables immediate, guided support at the point of referral, thus enabling patients to manage their symptoms independently whilst waiting for treatment to begin. We know from our preliminary work that using the Wysa app at the onboarding stage is likely to result in improved outcomes for those who engage highly [10]. This research will also add to the findings of an ongoing RCT looking at the effectiveness of the Wysa app as a mental health support tool for NHS talking therapies patients waiting for therapy. When considering the application of AI to mental wellbeing, the ability to feel listened to is the most influential factor in patient satisfaction

Version number 1.1 - 25th November 2023

and response. Users need to feel able to share their thoughts with the AI and our user testimonials show that the anonymous nature of this text-based interaction is imperative to them, even though they know they are communicating with an AI chatbot.

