8.2.4 Outcomes

8.2.4.1 Primary Outcomes

In order to understand the impact of Wysa therapeutics across the care pathway we will be conducting two distinct analyses. In Part 1 we will be focusing on e-triage and in Part 2 we will be focussing on the waitlist support and cCBT programmes.

The primary analysis in Part 1 will be a comparison of the time spent by the clinician to make a decision on the treatment pathway for those who complete the Wysa e-triage, with that taken to make a decision for patients who do not. The primary outcome measure will be time taken for the clinician to make a decision, for each of these two assessment pathways.

The primary analysis in Part 2 will be a comparison of depression and anxiety scores before and after a Wysa intervention (waitlist self care or step 2 cCBT). The primary outcomes will be measured at onboarding, start of intervention and discharge from intervention. In line with the national recommendations laid out by the NHS talking therapies Manual, we will be using Wysa's AI automation to encourage users to complete the Patient Health Questionnaire (PHQ-9 [15) and General Anxiety Disorder (GAD-7 [16]) routine outcome measures.

	Primary Outcome	Outcome Measure
Part 1: E-triage	Clinical Time Savings	Hours/Minutes
Part 2: Waitlist and cCBT	Depression or Anxiety severity	Score on the PHQ9 and GAD7

Table 5. Primary Outcome Measurement

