8.3.3 Recruitment

8.3.3.1 Participant Identification

Part 1: All Participants who are referred, or refer themselves to NHS talking therapies for mental health support and are accepted for an NHS talking therapies intervention, and who meet the inclusion criteria, will be eligible to be a part of the study.

Part 2: All participants who are accepted onto the step 2 care pathway, who meet the inclusion criteria and agree to engage in a Wysa cCBT programme will be eligible to participate in the study.

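### Part 1's primary time comparison covers accepted patients only and groups them by completing e-triage, so case mix may bias it and it cannot show a saving per referral

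*Protocol*

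**What the plan says.** **Population.** Protocol section 8.3.2.2 states for Part 1: "Participants will be all patients who self-refer or are referred to an NHS talking therapies service and accepted into the service". Section 8.3.3.1 repeats the condition for patients who "are accepted for an NHS talking therapies intervention", and section 8.3.2.1 makes acceptance a condition for the study as a whole.

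**Contrast.** The Part 1 primary analysis in section 8.2.4.1 compares clinician time among "those who complete the Wysa e-triage, with that taken to make a decision for patients who do not". The outcome is fixed in the same section: "The primary outcome measure will be time taken for the clinician to make a decision, for each of these two assessment pathways". Section 6 words the comparator more narrowly, setting the time after a completed e-triage against that "with the time taken when a standard assessment is undertaken".

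**Expected mechanism.** Section 7.2 predicts time savings mainly because much of the assessment moves into the app. It adds that the tool "may also reduce the number of inappropriate referrals", by directing complex, ineligible or high-risk users elsewhere sooner.

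**Safeguards.** Section 8.3.2.1 says there is no control arm. Section 8.5 names only descriptive and comparative statistics. Section 9.1 says that analysing all participants avoids recruitment bias.

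**The concern.** Two selections are built into the primary contrast, and both follow the start of e-triage.

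The first is completion. Whether a patient completes is known only after the e-triage has been opened. On the literal wording of section 8.2.4.1, someone who opens it, gives up and then needs a standard assessment is counted against the standard pathway. If such patients take more clinician time than average, the comparator is lengthened and the cost of unfinished e-triage is charged to the wrong side. If they take less, the error runs the other way.

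The second is acceptance. It is partly a result of the very decision whose duration is measured. Because section 7.2 expects the tool to redirect some users, the accepted patients on the two pathways may differ in case mix. Clinician time on referrals that are not accepted is never counted.

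This is one of two primary analyses. Section 5 lists service efficiency among the aims, and section 10.1 says the data will support regulatory approval and wider adoption. A reader could easily take the result as the time a service saves per referral, which it is not.

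**Working it through.** The protocol gives no clinician times, e-triage uptake, completion rates or acceptance rates, so there is no planned figure to reproduce. **Every input below is an assumption.** In steps 1 to 4, 70% of referrals are simple (40 minutes), 30% are complex (80 minutes), and e-triage changes nobody's time. The true saving is therefore 0.

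**Step 1. Completion, literal reading of section 8.2.4.1.** Half of each type open the e-triage. With completion rates c_s (simple) and c_c (complex), completers are 0.5 × 0.7 × c_s simple and 0.5 × 0.3 × c_c complex. Everyone else is the comparator. For 80% and 50%:

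- Completers: (40 × 0.28 + 80 × 0.075) / 0.355 = 48.5 minutes
- Comparator: (40 × 0.42 + 80 × 0.225) / 0.645 = 54.0 minutes
- Apparent saving: 5.5 minutes

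| Completion, simple / complex | Completers | Comparator | Apparent saving |
|---|---|---|---|
| 70% / 70% | 52.0 | 52.0 | 0.0 |
| 70% / 60% | 50.7 | 52.6 | 1.9 |
| 80% / 50% | 48.5 | 54.0 | 5.5 |
| 80% / 30% | 45.5 | 55.1 | 9.6 |
| 50% / 80% | 56.3 | 50.2 | −6.1 |

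The last row, (40 × 0.175 + 80 × 0.12) / 0.295 against (40 × 0.525 + 80 × 0.18) / 0.705, shows that the sign depends on who completes.

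**Step 2. Comparator as worded in section 6.** Suppose patients with incomplete e-triage are dropped instead. At 80% and 50%, completers average 48.5 minutes and those who never opened it average 0.7 × 40 + 0.3 × 80 = 52.0. A spurious 3.5 minutes remains, so the narrower wording does not cure the problem.

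**Step 3. Grouping by pathway started.** With the same inputs, those who opened e-triage average (40 × 0.35 + 80 × 0.15) / 0.5 = 52.0 minutes, as do those who did not. The difference is 0, but only because opening was assumed unrelated to complexity. If 55% of simple and 40% of complex patients open it, the means are (40 × 0.385 + 80 × 0.12) / 0.505 = 49.5 and (40 × 0.315 + 80 × 0.18) / 0.495 = 54.5, a spurious 5.0 minutes. This grouping removes completion selection but not self-selection into starting.

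**Step 4. Acceptance and case mix.** Let all simple cases and a share a of complex cases be accepted, with everyone completing. Mean time is (40 × 0.7 + 80 × 0.3a) / (0.7 + 0.3a).

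- a = 60% on both pathways: 48.2 against 48.2, difference 0
- a = 40% under e-triage, 60% under standard assessment: 45.9 against 48.2, apparent saving 2.3 minutes
- a = 30% and 70%: apparent saving 4.7 minutes

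Acceptance therefore distorts the contrast only if it differs between pathways.

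**Step 5. Accepted-only against per-referral saving.** Now let accepted patients take 60 minutes under standard assessment and 50 under e-triage, so that the plan reports 10. With r the share not accepted and t the minutes spent on each such referral, the per-referral saving is [(1 − r_std) × 60 + r_std × t_std] − [(1 − r_e) × 50 + r_e × t_e].

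| r, e-triage / standard | t, e-triage / standard | Saving per referral |
|---|---|---|
| 20% / 20% | 40 / 30 | 54 − 48 = 6.0 |
| 20% / 20% | 30 / 30 | 54 − 46 = 8.0 |
| 20% / 20% | 5 / 40 | 56 − 41 = 15.0 |
| 30% / 10% | 5 / 40 | 58 − 36.5 = 21.5 |

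The accepted-only figure can overstate or understate the saving per referral.

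**The case against.** The best defence is that accepted patients are a coherent population for timing a decision on treatment pathway, and that acceptance applies to both groups. Section 7.2's main predicted saving, assessment through the app, can be observed in accepted patients. A reader might infer that the rationale places the saving wholly in referrals that are not accepted. It does not: fewer inappropriate referrals is a separate and hedged expectation. This part of the defence stands, and it makes the acceptance restriction mainly a matter of a narrower target.

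It can also be said that section 8.2.4.1 speaks of two assessment pathways and section 6 of standard assessment, so the protocol does not clearly plan to compare completers with everyone else. That is fair. Neither section says where an incomplete e-triage belongs, and such detail could sit in an analysis plan that is not shown. But the only definition of the primary contrast turns on completion, and step 2 shows that dropping the incomplete cases is not neutral. Nor can a later plan recover clinician time on patients who were never enrolled.

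A reader might further infer that patients who abandon e-triage are more complex and that the saving is therefore inflated. That is plausible, but nothing in the protocol states it.

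Finally, a remedy that brings every non-accepted referral into the primary population would meet the consent requirement in section 8.3.1.1, the exclusions in section 8.3.1.2 and the consent text in section 8.3.3.2. It would also need time data that the protocol does not say are recorded. This objection stands, and the fix is limited accordingly.

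**Conclusion.** The point holds in a limited form. The primary Part 1 contrast is fixed by completion of e-triage, and its population by acceptance. If completion is related to complexity, the estimated saving is biased. If acceptance differs between pathways, the two accepted groups may differ in case mix. In either case the result describes accepted patients and not referrals. The assurance in section 9.1 does not answer this, because the participants it refers to have already been selected.

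The size and net direction cannot be derived from the protocol. The figures above (−6.1 to 9.6 minutes from completion, 0 to 4.7 from differential acceptance, and 6.0 to 21.5 per referral against 10 in accepted patients) only illustrate the mechanisms under assumed inputs. Bias from completion is zero if completion is unrelated to complexity. It would be too strong to say that the plan is known to inflate the saving, or that regrouping makes the comparison unbiased. For a feasibility review without a control arm, this is a should-fix.

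**What to change.** 1. Amend Protocol sections 6 and 8.2.4.1 so that the primary grouping is by assessment pathway started: e-triage opened against standard assessment. Count all clinician time for a patient with an incomplete e-triage, including any standard assessment that follows, in the e-triage group.
2. Adjust the comparison for baseline PHQ-9 and GAD-7, referral route and site. Keep the completer comparison as a secondary analysis.
3. State that the primary result applies to accepted patients and is not a service saving per referral.
4. Where the consent and data-access basis allows, and where the time is recorded, report by pathway the number of non-accepted referrals and the clinician time spent on them, as aggregate service data.

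**Cost.** Items 1 to 3 are changes of text and analysis. Section 6 already plans to review e-triage engagement data, so starting should be identifiable, but the sponsor must confirm that an unfinished e-triage can be linked to the later assessment. Baseline scores may be missing when the e-triage was not finished. Item 4 depends on permissions and records that the protocol does not describe. The estimated saving may come out smaller, and because patients still choose whether to start e-triage, the result remains observational and should be reported as such.

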8.3.3 Recruitment

8.3.3.1 Participant Identification

Part 1: All Participants who are referred, or refer themselves to NHS talking therapies for mental health support and are accepted for an NHS talking therapies intervention, and who meet the inclusion criteria, will be eligible to be a part of the study.

Part 2: All participants who are accepted onto the step 2 care pathway, who meet the inclusion criteria and agree to engage in a Wysa cCBT programme will be eligible to participate in the study.

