5 STUDY SUMMARY

Table 3. Study Summary

Study Title	The benefits of adopting WYSA therapeutics for patients, clinicians, services and the wider health care system.	
Short title	An evaluation of Wysa therapeutics	
Study Design	The study proposed is a real world quantitative evaluation to investigate the impact of Wysa therapeutics on clinical outcomes, and the experience of using the products in people with mild to moderate common mental health disorders. Outcome measures will include client satisfaction questionnaires and PHQ9 and GAD7 scores, as well as clinical and/or administrative time savings.	
Study Participants	The target population of the will include individuals over the age of 16 years who are referred, or self-refer, to Improving Access to Psychological Therapies programme (NHS talking therapies) for mental health support.	
Planned Size of Sample	The planned sample size is 100 individuals from 5 provider sites, two run by Dorset University Healthcare NHS Foundation Trust and three run by Lanchashire and South Cumbria NHS Foundation Trust.	
Follow up duration	N/A	
Planned Study Period	The study will last 18 months which includes three months of evaluation refinement, ethical approval, technical integration and testing. A further three months will be required for analysis of some secondary outcomes and preparation for dissemination.	
Research Question/Aim(s)	 The study aims are as follows: 1. To establish real-world evidence of the effectiveness of Wysa as a referral and triage tool. 2. To establish the impact of Wysa as a self help mental health support tool for patients waiting for treatment. 3. To establish the effectiveness of therapist enabled Wysa cCBT interventions on mental health outcomes. 4. To evaluate user experience of the range of Wysa therapeutics. 5. To establish if the adoption of Wysa therapeutics results in any service related efficiencies, for example clinical or administrative time savings. 	

The main research question is: How do the range of Wysa therapeutic tools benefit patients, clinicians, services and the wider health care system?
health care system?

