From here the patient will be offered the opportunity to download the Wysa app as a waitlist support tool until they are offered an intervention. The Wysa app includes over 150 self care tools, conversational AI and daily check-ins and reminders via push notifications. We will analyse data collected from within the app to understand app usage and any effect use of the app may have on mental wellbeing markers during the wait period.

Patients who are then offered Wysa's cCBT by their assessing clinician will have access to diagnosis specific weekly web or app based programmes including psychoeducational videos and CBT conversational techniques, as well as periodic reviews by an NHS talking therapies clinician through a communication dashboard called the Therapist Companion, which is also fully integrated into the service EPR system. We will report on changes in clinical outcome measures and engagement metrics to understand the efficacy of these cCBT programmes.

For all patients using Wysa within the service there is a built in SOS response. Wysa has three pathways to crisis alert and response:

- Patients are able to trigger crisis help by selecting the 'SOS' button on the app.

Version number 1.1 - 25th November 2023

- Crisis response will be triggered by responses to PHQ9 question 9
- Crisis response will be triggered when risk language is used (and confirmed by the chatbot) within free text.

When Wysa or the user triggers the crisis response pathway, users will be offered to complete a safety plan, engage in grounding exercises, and be provided with local or national crisis helplines. We will collect data including the number of times that the Wysa SOS response is triggered, the number of false positives identified by the AI, and SOS tool usage.

After patients have been discharged, Wysa can also be used as a support/ relapse prevention tool. All participants will have access to the AI Chatbot and self tools for 12 months from onboarding.

[figure not shown]

Figure 1. Current NHS talking therapies care pathway flows including Wysa therapeutics.

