8 METHODS

8.1 Study Design

A quantitative evaluation will be used to understand the impact of Wysa's application at key points in the patients' care pathway:

- At referral
- Whilst waiting for treatment
- As an intervention

The evaluation will include an analysis of app usage data and clinical outcome data, in order to establish engagement levels with Wysa therapeutics, as well as Wysa's efficacy at improving mental health outcomes.

The study will be comprised of two parts:

Part One: Evaluation of Wysa e-triage

Part Two: Evaluation of Wysa self-help tools as waiting list support and Wysa cCBT programmes

[figure not shown]

Figure 3: Participant flow Diagram

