8.2 Study Context

8.2.1 Participants

The target population of the study will include patients who are 16+ who are referred, or self-refer to NHS talking therapies adult mental health services for support, and who at any stage of their NHS talking therapies journey, download and use any of the Wysa functionality.

The cCBT programmes will be accessed by a subset of the patients who are accepted for step 2 treatment. Step 2 treatment is usually offered to patients experiencing mild or moderate depression and/ or anxiety symptoms as recommended by NICE guidelines for stepped care in NHS talking therapies services.

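### Part 2 is meant to evaluate waitlist self care, but its recruitment rule admits only patients who agree to a Wysa cCBT programme

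*Protocol*

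**What the plan says.** Section 8.1 defines the second part of the study as "Part Two: Evaluation of Wysa self-help tools as waiting list support and Wysa cCBT programmes". Section 8.2.4.1 makes its primary analysis a "comparison of depression and anxiety scores before and after a Wysa intervention (waitlist self care or step 2 cCBT"), with PHQ-9 and GAD-7 taken at onboarding, at start of intervention and at discharge. Aim 2 in the Study Summary (section 5) is "To establish the impact of Wysa as a self help mental health support tool for patients waiting for treatment".

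Two sections say who enters Part 2:

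- 8.3.2.2: "Participants will be patients who are accepted onto the Step 2 waiting list and consent to digital treatment".
- 8.3.3.1: eligible are "All participants who are accepted onto the step 2 care pathway, who meet the inclusion criteria and agree to engage in a Wysa cCBT programme".

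Section 8.2.1 adds: "The cCBT programmes will be accessed by a subset of the patients who are accepted for step 2 treatment".

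**The concern.** The part of the study that evaluates waitlist support has a recruitment rule based on a treatment that comes after, or late in, the wait. This raises two problems.

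- **Population.** A patient who uses the app while waiting and then receives something other than Wysa cCBT belongs to the group named in aim 2, but is not eligible for the comparison meant to answer it.
- **Timing.** If agreement to cCBT is given after the onboarding score, whether a patient counts can depend on how the wait went. Losing patients who worsen and are moved to another treatment would flatter Wysa. Losing patients who improve and decline cCBT would do the opposite. Section 8.3.2.1 states that there is no control arm, so nothing in the before-after mean would offset either effect.

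**Working it through.** The protocol gives no figure on this point to reproduce, so the check sets its statements side by side.

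**1. Who is waiting, and who is admitted.** Consider patients who onboard the app and are accepted by the service.

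| Patient | In the aim 2 group | Part 2 under 8.3.2.2 | Part 2 under 8.3.3.1 |
|---|---|---|---|
| Accepted onto Step 2, agrees to Wysa cCBT | yes | yes | yes |
| Accepted onto Step 2, declines cCBT or is treated another way | yes | depends on what digital treatment means | no |
| Accepted onto Step 2, stepped up before agreeing to cCBT | yes | yes, if consent to digital treatment came first | no |
| Accepted by the service, never on the Step 2 list | yes | no | no |

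The two rules differ in rows two and three, so two sites could enrol different populations and both comply. Section 8.2.1 says cCBT users are a subset of those accepted for Step 2, so the protocol itself expects row two to be occupied.

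**2. Order of events.**

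- The download link goes out on referral (sections 6 and 8.2.3).
- Scores start at e-triage or, failing that, at onboarding, and then follow every two weeks while the patient is engaged with the app (8.4.1).
- Section 6 says "the patient will be offered the opportunity to download the Wysa app as a waitlist support tool until they are offered an intervention".
- On cCBT, section 6 says: "Where the clinician has identified that a Wysa cCBT programme is an appropriate treatment intervention, this will be prescribed via an additional download link".

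No section says when agreement to cCBT is given or recorded. There are two cases:

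- Agreement at assessment: the stretch from referral to assessment can precede entry, and the later wait for treatment follows it.
- Agreement when treatment is offered: the whole wait can precede entry.

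In both cases the onboarding score can be earlier than the event that decides eligibility. How much earlier is not fixed.

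**3. Which comparison is affected.** The three measurement times give a waitlist interval (onboarding to start of intervention) and a treatment interval (start of intervention to discharge). Agreement to cCBT necessarily comes before the cCBT programme starts, so entry precedes baseline in the treatment interval and that comparison is sound on this point. Only the waitlist interval is affected.

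**4. Size.** A bias estimate would need the share of waitlist users who agree to cCBT, the spread of the scores, and the relation between change during the wait and agreement. The protocol gives none of these. Its one related figure is the minimum of 100 patients in 8.3.2.1, which is a whole-study minimum and does not help. Neither sign nor size can be derived.

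**The case against.** The strongest reply is that the rest of the protocol is wider than this one sentence:

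- 8.2.1 targets users of any Wysa function at any stage.
- 8.3.2.1 makes every accepted patient who meets the inclusion criteria eligible for the study.
- 9.1 puts all participants into the quantitative analyses.
- Section 6 plans to analyse app data from the wait with no cCBT condition.
- 8.2.4.1 joins the two interventions with an 'or', which leaves room for waitlist-only users.
- 8.4.1 gives Part 2 participants weekly scoring, as if Part 2 were sometimes shorthand for the cCBT phase.

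These points show that the narrow rule may not be intended. They also rule out one inference a reader might draw, that waitlist-only users are shut out of the study altogether: Part 1 and the general eligibility text admit them. But none of these statements cancels the Part 2 condition in 8.3.3.1, and 9.1 reaches only patients already admitted.

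A second reply is that the timing is inferred. Section 6 has cCBT offered by the assessing clinician, and 8.3.2.2 places entry at acceptance onto the waiting list, so agreement could come at assessment. The participant flow and care pathway figures, which might settle it, are not shown in the text available. This stands: selection after baseline is possible, not stated. A reader might go further and infer that the waitlist result will be biased in Wysa's favour. The documents do not support that, because both the time of agreement and the direction of any selection are unknown.

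Third, the study calls itself a feasibility review, and comparisons with non-users are also planned (section 6 and 8.5). Those comparisons would not undo selection among Wysa users. Nor is this only SAP detail: the recruitment rule is fixed in the protocol, and its sections disagree.

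**Conclusion.** The concern holds as an inconsistency in the protocol's own eligibility text, with a consequence for one of the two primary before-after comparisons in Part 2. If 8.3.3.1 is followed as written, the onboarding-to-start-of-intervention result describes future cCBT users and not the patients waiting for treatment in aim 2. That conclusion needs no assumption about timing.

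The further point, that entry may depend on events after the onboarding baseline, is a possibility. It rests on app access from referral and on the absence of a stated time for agreement to cCBT. No figure can be attached to it, and it should not be presented as a demonstrated bias in either direction. The start-to-discharge cCBT comparison is not affected.

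**What to change.** In 8.3.2.2 and 8.3.3.1, use one consistent rule and define two Part 2 sets:

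1. **Waitlist set:** all consenting patients accepted by the service (as in 8.3.2.1) who meet the inclusion criteria and onboard the app. Baseline is onboarding. Patients stay in the set regardless of later step-up or agreement to cCBT.
2. **cCBT set:** patients accepted onto Step 2 who agree to a Wysa cCBT programme. Baseline is start of intervention.

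Report how many in the waitlist set step up, decline cCBT or have no later score.

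The cost is wording in two sections and three counts, with no new data collection. There are downsides. Scores are collected only while the patient is engaged with the app (8.4.1), so some of the waitlist set will lack a later score, and the mean change may look less favourable. Acceptance by the service can itself follow onboarding, so some dependence on later events may remain; the condition is kept because 8.3.2.1 confines the study to accepted patients. I would not fill the gaps by rule with the last available app score, since that ties length of follow-up to engagement.
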